8.2 Echocardiographic, Clinical and Functional Endpoints

8.2.1 Echocardiographic Endpoints and Parameters

Echocardiographic data will be evaluated by a core laboratory. TTE parameters will be assessed at baseline, discharge, 30 days, 6 months, 1 year and annually until 5 years post procedure. TEE parameters will be assessed at start and end of implant procedure. The change from baseline for selected items will be presented as shift from baseline for each of the pre-specified follow-up periods. Patients that are missing a baseline or follow-up values will be excluded from the analysis.

8.2.2 Clinical and Functional Endpoints and Parameters

All-cause mortality rates at 30 days, 6 months, 1 year, and annually thereafter and corresponding 95% confidence intervals will be computed using the Kaplan-Meier algorithm with the standard errors being computed using Greenwood's formula.

Heart failure re-hospitalization rates at 30 days, 6 months, 1 year, and annually thereafter will be summarized with counts and percentages.

Re-intervention rates for tricuspid regurgitation at 30 days, 6 months, 1 year and annually thereafter will be summarized with counts and percentages.

Composite of major adverse events (MAE) defined as cardiovascular mortality, MI, stroke, renal complications requiring unplanned dialysis or renal replacement therapy, severe bleeding, unplanned or emergency re-intervention (either percutaneous or surgical) related to the device and major access site and vascular complications requiring intervention at 6 months, 1 year and annually thereafter will be summarized with counts and percentages.

 Edwards	Revision Date: January 22, 2019		Rev	For Use Only by Affiliates of Edwards Lifesciences	Page 23 of 25
	Title		Statistical Analysis Plan for Edwards CLASP TR EFS		

Change from baseline in NYHA Functional Classification and Edema assessment at 30 days, 6 months, 1 year and annually thereafter will be presented as shift from baseline for each of the pre-specified follow-up periods. Patients that are missing a baseline or follow-up values will be excluded from the paired analysis.

Change from baseline in Quality of Life (QoL) score, as measured by Kansas City Cardiomyopathy Questionnaire (KCCQ), Short Form Health Survey (SF-36) and six minute walk test (6MWT) as well as weight, ankle circumference measurement and patient edema questionnaire at 30 days, 6 months and corresponding follow-up visits will be summarized by mean and standard deviation. Patients that are missing a baseline or follow up values will be excluded from the analysis. For the analyses of 6MWT, patients unable to perform the walk due to a medical reason will be considered to have walked an actual distance of zero. eDiary assessments and Activity Monitoring will be summarized using descriptive statistics based on data types and for each pre-specified follow-up periods.

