## **6 STUDY DESIGN**

This is a prospective, single arm, multi-center, early feasibility study designed to evaluate the safety and performance of the PASCAL System in the treatment of symptomatic severe tricuspid regurgitation (TR).

Up to 65 patients (pending FDA approval) will be enrolled in the study at up to 30 investigational sites (pending FDA approval) in the US. All enrolled study patients will be assessed for clinical follow-up at the following intervals: discharge, 30 days, 6 months, 1 year, and annually for 5 years post implant procedure.

A description of each study visit and required study procedures are included in Section 8, Procedures and Methods. In addition, a summary of required procedures is listed in Table 11.

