2.2 Overall Study Design and Plan

This is a prospective, single arm, multi-center, early feasibility study designed to evaluate the safety and performance of the PASCAL System in the treatment of symptomatic severe regurgitation (TR).

 Edwards Lifesciences	Revision Date: January 22, 2019		Rev	 For Use Only by Affiliates of Edwards Lifesciences	Page 8 of 25
	Title	Statistical Analysis Plan for Edwards CLASP TR EFS			

A total of 15 patients will be enrolled in the study at up to 8 investigational sites in the US. All enrolled study patients will be assessed for clinical follow-up at the following intervals: discharge, 30 days, 6 months, 1 year and annually for 5 years post implant procedure.

A description of each study visit and required study procedures is included in the clinical protocol's Section 8, Procedures and Methods. In addition, a summary of required procedures is listed in Table 11, Schedule of Assessments of the clinical protocol.

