6. STATISTICAL ANALYSIS

6.1 General Conventions

- For continuous variables, data will be summarized using the number of observations, mean, median, standard deviation, minimum, maximum, and 95% confidence intervals (based on normal distribution) per table shells. Nonparametric techniques may be used if the data

 Edwards Lifesciences	Revision Date: January 22, 2019		Rev 	For Use Only by Affiliates of Edwards Lifesciences	Page 15 of 25
	Title	Statistical Analysis Plan for Edwards CLASP TR EFS			

does not meet the assumptions of parametric tests.

- For categorical variables, data will be summarized using the number of observations, percentage, and 95% Clopper-Pearson confidence intervals per table shells. In general, the denominator for the percentage calculation will be based on total number of patients with evaluable data for a specified time point unless otherwise specified. Patients with missing data will be excluded from the denominator.
- For time-to-event variables, survival analysis will be used to analyze the data. Summaries will include the number of patients at risk, and number of patients with the event. Patients without events will be censored at their last known event-free time point. If this event-free time point occurs after the analysis time point, the days to event variable will be set equal to the analysis time point so that the patient will be included in the analysis. For patients who did not have an event or early withdrawal and have not yet completed the analysis visit, they will be censored at their last information date. Time to first event curves will be constructed using Kaplan-Meier estimates and all post procedure results will be summarized with Kaplan-Meier estimates of event rates. Hazard ratios, confidence interval for the hazard ratios, and p-values may also be presented from a Cox proportional hazards model.
- For selected variables, in addition to descriptive summary statistics at each follow-up assessment, change from baseline to subsequent time point will be summarized. Paired (i.e., patients with available data at both baseline and respective time point) and unpaired data will be presented separately for selected variables. In general, patients with missing baseline or following-up values will be excluded from the analysis unless otherwise specified.

 Edwards	Revision Date: January 22, 2019		Rev	 For Use Only by Affiliates of Edwards Lifesciences	Page 16 of 25

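### SAP 8.2.2 gives Kaplan-Meier/Greenwood intervals for all-cause mortality but names neither the scale of the limits nor a rule for zero deaths, so a study with no deaths has no usable interval

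*SAP*

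**What the plan says.** SAP 8.2.2 covers "All-cause mortality rates at 30 days, 6 months, 1 year, and annually thereafter". For all of these time points, "95% confidence intervals will be computed using the Kaplan-Meier algorithm with the standard errors being computed" by Greenwood's formula. The SAP names no transformation (plain, log or log-log) and no fallback for a time point without deaths. SAP 9.1 refers the summary of deaths back to 8.2.2, so this is the only all-cause mortality interval that the SAP plans.

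SAP 6.1 sets "95% Clopper-Pearson confidence intervals per table shells" for categorical variables. SAP 8.1 asks for a 95% interval for the 30-day MAE percentage and for each MAE component, and cardiovascular mortality is one of these components (SAP 3.1). SAP 8.1 does not name the method again, so the Clopper-Pearson convention of 6.1 applies by implication.

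Protocol 12.5 allows either a binary proportion or Kaplan-Meier for all-cause mortality and does not specify an interval.

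The sample size differs between the documents. Protocol section 6 says "Up to 65 patients (pending FDA approval) will be enrolled in the study". SAP 2.2, written for protocol version A, says "A total of 15 patients will be enrolled in the study at up to 8 investigational sites in the US". Both sizes are used below.

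**The concern.** Greenwood's formula builds the variance from the deaths. With no deaths there is nothing to sum, and the formula returns a variance of zero, whatever the sample size. A 0% to 0% interval reads as certainty when the data still allow several percent mortality, and a blank cell gives the reader nothing.

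The result would also be inconsistent within one report. With no deaths by 30 days, the safety table would show cardiovascular death with an exact upper limit above zero. The mortality table would show all-cause death, which includes cardiovascular death, as 0% to 0% or undefined for the same patients. A part cannot have a larger upper limit than the whole.

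The protocol describes this as the first US study with the system and lists guidance for future study designs among its objectives. The uncertainty around early mortality is therefore a figure that readers will use.

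**Working it through.** The documents state no mortality rate, interval or precision target, so there is no planned figure to reproduce.

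**Inputs.** n = 65 (protocol section 6) and n = 15 (SAP 2.2); 95% confidence, z = 1.96 (SAP 8.2.2). The true 30-day risk p is an assumption, taken as 1% to 3%, because the public text gives none. No censoring unless stated.

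**Greenwood.** With S the Kaplan-Meier survival estimate, SE = S × √(Σ dᵢ / [nᵢ(nᵢ − dᵢ)]). Without censoring this equals √(q(1 − q)/n), where q = d/n.

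**No deaths.** Every dᵢ is 0, so SE = 0.
- Plain scale: 0 ± 1.96 × 0, that is 0% to 0%.
- Log-log scale: the standard error is divided by |ln S| = |ln 1| = 0, so the limits are undefined.
- Exact (Clopper-Pearson) upper limit: 1 − 0.025^(1/n), which is 5.5% at n = 65 and 21.8% at n = 15.

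**How likely no deaths is.** P(0 deaths) = (1 − p)^n.

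| True risk (assumed) | n = 65 | n = 15 |
|---|---|---|
| 1% | 52.0% | 86.0% |
| 2% | 26.9% | 73.9% |
| 3% | 13.8% | 63.3% |

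**One or more deaths, by scale.** Without censoring, the plain lower limit is negative when d < z²n/(n + z²), which is 3.63 at n = 65 and 3.06 at n = 15, so for one to three deaths at either size.

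| Deaths / n | Plain | Log-log | Clopper-Pearson |
|---|---|---|---|
| 1/65 | -1.5% to 4.5% | 0.2% to 10.4% | 0.04% to 8.3% |
| 2/65 | -1.1% to 7.3% | 0.8% to 11.8% | 0.4% to 10.7% |
| 3/65 | -0.5% to 9.7% | 1.5% to 13.6% | 1.0% to 12.9% |
| 1/15 | -6.0% to 19.3% | 1.0% to 38.7% | 0.2% to 32.0% |
| 3/15 | -0.2% to 40.2% | 6.9% to 50.0% | 4.3% to 48.1% |

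The log scale is also negative for one to three deaths at n = 65 (-1.5%, -1.2%, -0.6%). With early censoring the count can shift. With 13 of 65 censored before the first death, the plain lower limit is still negative for one to three deaths. With 3 of 15 censored first, it is negative for one and two deaths but +0.5% for three.

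**Coverage.** This is the sum of the binomial probabilities of the death counts whose interval contains p. An undefined interval counts as a miss.

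| n, p | Plain | Log-log | Plain, exact at 0 deaths | Log-log, exact at 0 deaths | Clopper-Pearson |
|---|---|---|---|---|---|
| 65, 1% | 47.9% | 45.2% | 99.9% | 97.2% | 99.6% |
| 65, 2% | 72.9% | 69.0% | 99.8% | 95.9% | 99.0% |
| 65, 3% | 85.9% | 81.6% | 99.7% | 95.4% | 98.7% |
| 15, 1% | 14.0% | 13.0% | 100.0% | 99.0% | 99.0% |
| 15, 3% | 36.6% | 29.4% | 99.9% | 92.7% | 99.1% |

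The plain column is almost exactly 1 − P(0 deaths): for example 1 − 13.8% = 86.2% against 85.9%. At these risks, the loss of coverage comes from the samples without deaths.

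**The case against.** **The scale is not stated.** Greenwood gives a variance, not a scale. A reader might infer that the SAP plans untransformed limits and so will print negative lower limits. The text does not support this: log-log limits use the same Greenwood variance, stay at or above zero, and are already permitted by the wording. This objection stands, and the negative limits are conditional.

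**The coverage figures can be over-read.** A reader might take 86% (n = 65) or 37% (n = 15) at a 3% risk as proof that the plain interval fails in general. At risks of 1% to 3% it does not: with an exact interval only at zero deaths, coverage is 99.7% or more. Switching to log-log alone would not help either, since it scores lower than plain while zero deaths remain unhandled. This also stands.

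**The report would still carry an exact interval.** No deaths at all means no cardiovascular deaths, and the 30-day MAE table should show 0% to 5.5% (0/65) for that component. This softens the consequence at 30 days. It does not repair the all-cause line and makes the two tables disagree.

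**Other provisions.** SAP 6.1 sends data to listings when they are insufficient for summary statistics, but no deaths among fully followed patients is a result, not a lack of data. Protocol 12.5 permits a binary proportion, but SAP 8.2.2 does not take up that option.

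**Importance.** All-cause mortality is listed among the clinical and functional endpoints, the safety endpoint is the MAE composite, and no decision rule uses the mortality interval. This stands and limits the weight of the point.

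**Conclusion.** The concern holds for zero deaths on either the plain or the log-log scale: the planned method gives 0% to 0% or no interval, where exact upper limits are 5.5% (0/65) and 21.8% (0/15). Under an assumed 30-day risk of 1% to 3% without censoring, this happens with probability 52% to 14% at 65 patients and 86% to 63% at 15. The n = 15 figures apply only if enrolment stays at the SAP's number; the current protocol allows up to 65.

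For one to three deaths the finding is weaker: the scale is unspecified, and a negative lower limit follows only if untransformed (or log) limits are used and early censoring is light.

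Mortality is descriptive and untested, so the effect is confined to the precision reported. It is still worth correcting before analysis, because the zero-death outcome is plausible and the SAP already contains a suitable method.

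**What to change.** Replace the interval rule in SAP 8.2.2 with the following:
- At 30 days, when every patient's status is known, report the Clopper-Pearson interval.
- At any time point with no deaths, report the Clopper-Pearson interval, using the number still at risk if there is censoring.
- Otherwise, report log-log Kaplan-Meier limits with the Greenwood variance.

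For risks of 1% to 3%, log-log limits with the exact interval at zero deaths cover about 95% to 97% at n = 65 and 93% to 99% at n = 15; Clopper-Pearson covers about 99%.

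The cost is a few lines of SAP text. Protocol 12.5 already allows either approach to the rate, so no protocol change is needed. The reported upper limits become wider and less favourable: at 1/65, 8.3% (exact) or 10.4% (log-log) instead of 4.5% (plain).

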## **12.7 Treatment of Missing or Spurious Data**

Unless otherwise specified, all analysis will be based on available data only.

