6.2 Handling of Missing Data

All statistical analysis on the endpoints will be performed using only those patients with available data required for endpoint analysis. No missing value imputation will be performed unless otherwise specified.

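### SAP 8.2.2 scores medical inability to walk as 0 m but by default leaves patients who died out of the 6MWT mean; the other functional and echo change summaries describe survivors with data without saying so

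*SAP*

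**What the plan says.** SAP 8.2.2 summarises change from baseline in KCCQ, SF-36, 6MWT, weight, ankle circumference and the edema questionnaire by mean and standard deviation. For this group, "Patients that are missing a baseline or follow up values will be excluded from the analysis". The next sentence gives the only special rule for a functional outcome: "patients unable to perform the walk due to a medical reason will be considered to have walked an actual distance of zero".

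NYHA class and edema grade are shown as shifts from baseline, and "Patients that are missing a baseline or follow-up values will be excluded from the paired analysis". For echocardiographic change, SAP 8.2.1 says "Patients that are missing a baseline or follow-up values will be excluded from the analysis".

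The general rules point the same way. For percentages, SAP 6.1 says "Patients with missing data will be excluded from the denominator". SAP 6.2 adds "No missing value imputation will be performed unless otherwise specified", and Protocol 12.7 has "Unless otherwise specified, all analysis will be based on available data only".

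None of these places mentions death, and SAP 8.2.2 does not say whether death is a medical reason for not walking. Deaths are reported elsewhere: Kaplan-Meier all-cause mortality with 95% intervals (SAP 8.2.2), and cardiovascular death within the MAE composite.

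Protocol Tables 9 and 11 schedule 6MWT, KCCQ and SF-36 through 1 year, and NYHA, edema and TTE through 5 years. The SAP, written for protocol version A, plans 15 patients; the current protocol (version C) allows up to 65.

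**The concern.** The zero-distance rule accepts that a walk missing because of illness is a bad outcome that should count. Death is a further step of the same illness, yet a patient who has died has no follow-up value and so falls under the exclusion rule. Followed as written, the 6MWT analysis treats being dead more favourably than being alive and unable to walk.

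For the other measures there is no such inversion, but the summaries silently become summaries of survivors with data. The study has one arm, so no comparator would reveal the effect of attrition. Protocol 7.1 expects patients like those in earlier experience, with mean ages of 78 and 75.6 years. One stated objective is to guide the design of later studies, and a survivor-only change read as the change in all treated patients could mislead that work.

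**Working it through.** The plan states no figure to reproduce: the public text has no expected mortality, baseline distance or gain. The clinical inputs below are therefore assumptions. Only N (15 from SAP 2.2, up to 65 from Protocol 12.1) comes from the documents.

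**1. Follow one patient through the rules.** Alive at the visit and medically unable to walk: distance 0 m, change −b, where b is the baseline. Dead before the visit: no follow-up value, no imputation, no stated exception, so excluded. The separate unpaired display, "Paired (i.e., patients with available data at both baseline and respective time point) and unpaired data will be presented separately for selected variables", does not help, because a patient who died has no value at that visit in either display.

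**2. Size of the inversion for one patient.** Let the other N−1 patients have mean change s.
- Scored 0 m: mean = [(N−1)s − b]/N.
- Excluded: mean = s.
- Difference = (s + b)/N, positive whenever s > −b.

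| N | b = 200, s = 0 | b = 250, s = 30 | b = 300, s = 50 |
|---|---|---|---|
| 65 | 200/65 = 3.1 m | 280/65 = 4.3 m | 350/65 = 5.4 m |
| 15 | 200/15 = 13.3 m | 280/15 = 18.7 m | 350/15 = 23.3 m |

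**3. What the silence on death is worth.** With D deaths among N patients, excluding them reports s. Treating death as a medical reason (0 m) reports [(N−D)s − D·b]/N. With s = +30 m and b = 200 to 300 m:

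| N | Deaths | Excluded | Scored 0 m |
|---|---|---|---|
| 65 | 3 | +30 m | +14.8 to +19.4 m |
| 65 | 6 | +30 m | −0.5 to +8.8 m |
| 65 | 13 | +30 m | −36 to −16 m |
| 15 | 1 | +30 m | +8.0 to +14.7 m |
| 15 | 2 | +30 m | −14.0 to −0.7 m |
| 15 | 3 | +30 m | −36 to −16 m |

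The last two columns are different quantities. The gap shows how far two programmers could differ under the same SAP text; it is not an estimate of bias.

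**4. Measures without a zero rule.** Here exclusion raises the reported change only if those who died would have changed less than the survivors. To show this in the same units, take N = 65, 6 deaths and survivors at +30 m. The full-cohort mean is (59 × 30 + 6c)/65, where c is the unobserved mean change in those who died:
- c = −50: 22.6 m
- c = 0: 27.2 m
- c = +30: 30.0 m
- c = +60: 32.8 m

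The survivor mean can therefore lie above, at or below the full-cohort mean.

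**5. Shift tables.** If 70% of survivors are in NYHA class I or II (assumed) and N = 65, the share of all 65 who are alive and in class I or II is 0.70 × (65 − D)/65: 66.8%, 63.5% and 56.0% for 3, 6 and 13 deaths. The survivor table shows 70% in every case.

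**The case against.** The strongest reply is that the SAP never says it drops the dead. Exclusion is inferred from the missing-value rule, and inability for a medical reason could be read to include death, in which case the 6MWT inversion disappears. The first part stands: this is a default that follows from silence, not a declared choice. The second does not settle the matter, because the two readings give very different results (step 3) and the SAP does not choose between them.

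A reader might go further and infer that dying improves every reported outcome, or that walk distance and KCCQ drift upward over 5 years. The documents support neither. The rise is certain only for 6MWT, against a 0 m score. Elsewhere it depends on an unobserved course (step 4), and TR grade after death is undefined rather than poor. 6MWT, KCCQ and SF-36 stop at 1 year, and exclusion criterion 33 removes patients with a life expectancy under 12 months, so the higher death counts in step 3 may be too pessimistic for these measures.

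Deaths are also not hidden. Kaplan-Meier mortality, MAEs, and disposition counts with a patient-level listing (SAP 7.1) are all planned. The analyses are descriptive, and no stated success criterion rests on these changes. Available-case summaries beside separately reported mortality are a legitimate choice. But a mortality curve does not show which baseline NYHA classes or TR grades the dead came from, so a reader cannot place them in the shift tables. The SAP also refers to table shells that are not in the public text; they may already show some of these counts.

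**Conclusion.** The point holds in a limited form and should be addressed. For 6MWT, through 1 year, the written rules by default place death above medical inability. The mean change rises by (s + b)/N for each 0 m score replaced by an exclusion: about 3 to 5 m at N = 65 and 13 to 23 m at N = 15, under the assumed baselines and changes. KCCQ and SF-36 through 1 year, and NYHA, edema and TTE through 5 years, are summaries of survivors with data. Upward bias in them is plausible but not shown. No test or decision rule is affected; what is at risk is how the results are read and carried into later designs. All metre and percentage illustrations rest on assumed mortality, baseline and gain.

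**What to change.** - **Label.** Keep the existing summaries, title them 'among survivors with data', and give the number dead and the number exited or missing at each visit.
- **Shift tables.** Add separate 'died' and 'exited/missing' columns for NYHA, edema and TR grade. Use all as-treated patients due at the visit as the denominator. Show ITT as well with non-implanted patients identified, since Protocol 7.4 has them exit after about 30 days of safety follow-up. For TR grade, the 'died' column is accounting, not a failure score.
- **6MWT rule.** State in SAP 8.2.2 that death is not handled as a missing walk.
- **Supportive analysis.** For 6MWT and KCCQ through 1 year, report the median change with death ranked worst, below medical inability for 6MWT.

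The cost is a few table columns and one extra analysis from data already collected. The reported improvement is likely to look less favourable.
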